2. STUDY OBJECTIVES

2.1. Part A (Single Dose)

Part A of the study will include participants 6 to 17 years of age (inclusive). Part A will be divided into 2 cohorts in this age range, Cohort 1 (12 to 17 years) and Cohort 2 (6 to 11 years).

2.1.1. Primary Objective:

- To characterize the PK of voxelotor in plasma and whole blood following a single dose in pediatric participants with SCD

2.1.2. Secondary Objective:

- To evaluate the safety and tolerability of voxelotor following a single dose in pediatric participants with SCD

2.2. Part B (Multiple Dose)

2.2.1. Primary Objective:

- The primary objective is to assess the efficacy of voxelotor in pediatric participants with SCD as measured by improvement in anemia

2.2.2. Secondary Objectives:

- To provide data on the ePRO measurement in establishing the longitudinal measurement properties of the PRO
- To evaluate the effect of voxelotor on clinical measures of hemolysis
- To characterize the PK of voxelotor in plasma, whole blood and red blood cells (RBCs) following multiple doses in pediatric participants with SCD
- To evaluate the safety and tolerability of voxelotor following multiple doses in pediatric participants with SCD
- To evaluate the effect of voxelotor on cerebral hemodynamics as assessed by TCD ultrasonography
- To evaluate the effects of voxelotor on SCD symptom exacerbation and total symptom score (TSS) from PRO measurement

2.3. Part C (Multiple Dose)

2.3.1. Primary Objective

- To evaluate the effect of voxelotor on cerebral hemodynamics in pediatric participants with SCD with elevated or conditional TCD flow velocity as assessed by TCD ultrasonography

2.3.2. Secondary Objective

- To evaluate the effect of voxelotor on clinical measures of anemia and hemolysis
- To characterize the PK of voxelotor in plasma, whole blood and RBCs following multiple doses in pediatric participants with SCD
- To evaluate the safety and tolerability of voxelotor following multiple doses in pediatric participants with SCD
- To evaluate the proportion of participants with normal TCD flow velocity (< 170 cm/sec by nonimaging TCD or < 155 cm/sec by TCDi) at 48 weeks
- To evaluate the effect of voxelotor on the incidence of stroke and vaso-occlusive crisis (VOC)

2.4. Part D (Multiple Dose)

2.4.1. Primary Objective

- To evaluate the safety and tolerability of voxelotor in pediatric participants with SCD aged 6 months to < 4 years

2.4.2. Secondary Objectives

- To characterize the PK of voxelotor in plasma, whole blood, and RBCs in pediatric participants with SCD aged 6 months to < 4 years
- To evaluate the effect of voxelotor on clinical measures of anemia and hemolysis in pediatric participants with SCD aged 6 months to < 4 years
- To evaluate the effect of voxelotor on the incidence of stroke and VOC in pediatric participants with SCD aged 6 months to < 4 years

2.4.3. Exploratory Objective

- To evaluate the effect of voxelotor on growth and development in pediatric participants with SCD aged 6 months to < 4 years

3. INVESTIGATIONAL PLAN

3.1. Study Design

This study is an integrated Phase 2a protocol consisting of 4 parts, Parts A, B, C, and D, which will explore single and multiple doses of voxelotor in pediatric participants with SCD. Pediatric participants who are 6 to 17 years of age will be included in Part A, 12 to 17 years of age in Part B, 4 to 17 years of age in Part C, and 6months to < 4 years of age in Part D.

3.1.1. Part A (Single-Dose Administration)

[figure not shown]
The Study Schematic for Part A is provided in [Figure 2](#). Approximately 12 pediatric participants with SCD will participate in Part A.

- Approximately 6 pediatric participants will be enrolled into Cohort 1: age 12 to 17 years, inclusive.
- Approximately 6 pediatric participants will be enrolled into Cohort 2: age 6 to 11 years, inclusive. Approximately 3 participants enrolled into the study will be between the ages of 6 to 8 years of age. Approximately 3 participants enrolled will be between the ages of 9 to 11 years of age.

Participants' age will be the age at the time of the assent/consent.

Following a 28-day Screening Period, voxelotor will be administered orally on Day 1 and participants will undergo PK sampling as indicated in the Schedule of Assessments ([Appendix 1](#)).

Figure 2: Part A Study Schematic

Upon completion of participation of Cohort 1 (12–17 year age group) and Cohort 2 (6–11 year age group) in Part A (Single Dose) of the study, participants may be eligible for participation in

Part B or Part C. If a participant from Part A wishes to participate in Part B or Part C, they will be required to complete screening procedures for Part B or Part C as appropriate. This will include re-consenting of eligible participants for participation in Part B or Part C of the study. Part B participants will not be eligible for participation in Part C. Please consult the Interactive Response System manual for further information.

3.1.2. Part B (Multiple-Dose Administration)

[figure not shown]
Upon satisfactory review of the safety and PK data in Part A as outlined in Section 3.5.1, Part B may commence. Approximately 36 pediatric participants with SCD who are 12 to 17 years of age will be evaluated.

- A minimum of 12 participants will be dosed with 900 mg. Enrollment at the 900 mg dose level may continue to further characterize the effect of multiple doses of voxelotor (not to exceed a total study size of approximately 36). A minimum of 6 of the participants at 900 mg will be 12 to 14 years old.
- Upon a favorable review by the DSMB, dosing a minimum of 6 participants at 1500 mg may commence (dependent on how many participants were enrolled at 900 mg, ie, not to exceed a total study size of approximately 36). Approximately half of the participants at 1500 mg will be 12 to 14 years old.

Participants' age will be the age at the time of the assent/consent.

Participants will receive multiple doses of voxelotor (up to 24 weeks). Following a 35-day Screening Period, pediatric participants will return to the clinic on Days 1, 2 and 8 and Weeks 2, 4, 8, 12, 16, 20, and 24 (refer to [Appendix 3](#)). On Study Day 1, participants will receive their first oral dose of voxelotor ([Figure 3](#)).

Figure 3: Part B Multiple-Dose Safety Study Schematic

3.1.3. Part C (Multiple-Dose Administration)

The Study Schematic for Part C is provided in [Figure 4](#). Up to 50 pediatric participants who are 4 to 17 years of age with SCD will be enrolled.

[figure not shown]
- At least 30 participants must have a TCD velocity ≥ 140 and < 200 cm/sec by nonimaging TCD (≥ 125 and < 185 cm/sec by TCDi) upon Screening AND
- At least 20 participants must be between 4 to 11 years of age

Participants' age will be the age at the time of the assent/consent.

During the 35-day screening period, participants will undergo TCD assessment and those who meet the criteria for TCD and the rest of the study eligibility criteria will be eligible for treatment and will receive multiple doses of voxelotor (up to 48 weeks).

Following completion of study treatment in Part C, eligible participants may be given the option to enroll in an open-label extension study (under a separate protocol) to receive voxelotor.

Figure 4: Part C Multiple-Dose Schema

Part C: Potential Modification

To further characterize a potential effect on TCD data for those participants who have a TCD velocity ≥ 140 and < 170 cm/sec by nonimaging TCD (≥ 125 and < 155 cm/sec by TCDi) upon screening, approximately 20 participants may be added with a TCD velocity that falls within this range, depending on the emerging data. In this event, Part C will contain up to 70 pediatric participants.

3.1.4. Part D (Multiple-Dose Administration)

The Study Schematic for Part D is provided in [Figure 5](#). Approximately 30 pediatric participants who are 6 months to < 4 years of age with SCD will be enrolled.

[figure not shown]
- At least 10 participants must be 6 months to < 2 years of age.

Participants' ages will be determined at the time of the assent/consent.

During the 35-day screening period, participants who meet the study eligibility criteria will be eligible for treatment and will receive multiple doses of voxelotor (for up to 48 weeks).

Following completion of study treatment in Part D, eligible participants may be given the option to enroll in an open-label extension study (under a separate protocol) to receive voxelotor.

Figure 5: Part D Multiple-Dose Study Schematic

3.2. Duration of Study

For Part A (single dose), participant participation is expected to last up to 44 days, including a 28-day Screening Period, one dosing day, and the 15-day follow-up visit.

For Part B (multiple dose), participant participation is expected to last approximately 33 weeks (including a 35-day Screening Period, a 24-week dosing period and an End-of-Study (EOS) visit approximately 4 weeks after the last dose of study drug).

For Part C (multiple dose), participation is expected to last approximately 57 weeks (including a 35-day Screening Period, a 48-week dosing period and an EOS visit approximately 4 weeks after the last dose of study drug for participants who do not enroll in the open-label extension study).

For Part D (multiple dose), participation is expected to last approximately 57 weeks (including a 35-day Screening Period, a 48-week dosing period, and an EOS visit approximately 4 weeks after the last dose of study drug for participants who do not enroll in the open-label extension study).

3.3. End-of-Study Visit

EOS procedures will be performed at the follow-up visit on Day 15 ± 1 day for Part A (single-dose portion), at $4 \text{ weeks} \pm 2$ days after the last dose of study drug (the EOS visit) for Part B and Part C (multiple-dose portion), and at $4 \text{ weeks} \pm 7$ days after the last dose of study drug (the EOS visit) for Part D (multiple-dose portion). For Parts C and D, the EOS visit will be performed for participants who do not enroll into the open-label extension study.

3.4. Early Termination Visit

Participants who terminate from the study early (early termination) will have EOS procedures performed at the time of discontinuation. Participants with ongoing clinically significant clinical or laboratory findings will be followed until the finding is resolved or medically stable; reasonable attempts will be made to follow-up with participants. The participant's participation will end once all study assessments and follow-up has been completed.

3.5. Ongoing Safety and Data Review

PK and safety data from study GBT440-007 will be reviewed on an ongoing basis.

The Sponsor will review PK and safety data from 6 participants enrolled in Part A (in the age group of 12 to 17 years) after the participants have undergone a minimum of 8 days of PK and safety data collection prior to proceeding to Part B of the study. In the event the PK exposure is not consistent with target exposure described in Section 1.5, the dose for Part B may be modified. Part B will not proceed until a formal review of the completed 8 days of PK and safety data of participants from Part A (in the age group of 12 to 17 years) occurs.

The Sponsor will also review PK and safety data from 6 participants enrolled in Part A (in the age group of 6 to 11 years) after the participants have undergone a minimum of 8 days of PK and safety data collection.

3.5.1. Part B Safety Requirements for Dose Escalation to the 1500 mg Treatment Arm

Prior to proceeding from the voxelotor 900 mg dose to the 1500 mg dose in Part B, the following will take place with data reviews confirming the selected dose to be generally well tolerated:

- A review of the PK data from at least 8 pediatric participants enrolled in Part B of Study GBT440-007 will take place, following at least 15 days of dosing with voxelotor 900 mg.
- DSMB review of safety data from at least 8 pediatric participants enrolled in Part B of Study GBT440-007 will take place, following the completion of 28 days of dosing with voxelotor 900 mg to confirm acceptable safety and tolerability.
- DSMB review of safety data from the first 6 adult participants at the 1500 mg dose level from Group 1 of Study GBT440-031 (HOPE study) will take place, following at least 28 days of dosing with study drug to confirm acceptable safety and tolerability.

The decision to proceed from the voxelotor 900 mg dose to the 1500 mg dose will be recorded in a dose decision document that will be signed by the GBT440-007 Study Director/Medical Monitor and relevant GBT personnel.

3.5.2. Part C

A DSMB monitors the safety and conduct of an ongoing Phase 3, GBT440-031 in adults and adolescents (aged 12–17 years) on a periodic basis. At a recent DSMB meeting safety data from 154 participants treated in GBT440-031 (randomized to placebo, 900 mg or 1500 mg) and 32 adolescents enrolled in this ongoing study, GBT440-007 (25 at 900 mg and 7 at 1500 mg) were reviewed. This safety review included 34 adolescents from GBT440-031. The DSMB agreed that the safety data supports continued treatment with both voxelotor 900 mg and voxelotor 1500 mg in GBT440-031 and in this study. The DSMB also agreed that the cumulative safety data from adults and adolescents supports the initiation of treatment of participants 4 to < 12 years old with voxelotor.

Safety data from children aged 4 to 11 years of age will be monitored on an ongoing basis by GBT. Additionally, the DSMB has reviewed safety data from Part C..

3.5.3. Part D

Safety data from children aged 6 months to < 4 years will be monitored on an ongoing basis by the Sponsor.

In addition, a DSMB may review safety data from Part D in consultation with the Sponsor if warranted (see Section 3.7).

3.6. Stopping Rules

Individual Participant Discontinuation

Dosing for any individual participant will be stopped if the participant experiences a SAE or a clinically significant nonserious AE, which in the opinion of the Principal Investigator or Sponsor's Medical Monitor, warrants discontinuation of the study for that participant's well-being.

Study Discontinuation

The occurrence of significant safety events will require that further dosing of participants be evaluated by the Medical Monitor to determine study discontinuation. Significant safety events may include those which are deemed to be related to study drug, have not been described in the voxelotor IB or otherwise represent a concern to the Investigator or the Sponsor.

3.7. Data and Safety Monitoring Board

An independent DSMB will monitor the safety and conduct of the trial. The DSMB membership will be composed of medical and statistical representatives. The DSMB may provide recommendations to the Sponsor regarding stopping the study or discontinuing a treatment arm or otherwise modifying the study design or conduct.

The DSMB for this study will review:

- Safety data from at least 8 pediatric participants enrolled in Part B of Study GBT440-007, following the completion of 28 days of dosing with voxelotor 900 mg to confirm acceptable safety and tolerability.
- Safety data on a periodic basis as defined in the DSMB Charter.

Sites will be informed of the DSMB recommendations only if the recommendations lead to changes in the study conduct.

The composition, responsibilities, and other details of the DSMB will be described in a DSMB Charter as appropriate for each part of the study.

Prior to proceeding from the 900 mg dose to the 1500 mg dose in Part B, the following DSMB review will also take place:

- A review of safety data from the first 6 adult participants at the 1500 mg dose level from Group 1 from the HOPE Study, following at least 28 days of dosing with study drug, to confirm acceptable safety and tolerability.

Part C: The DSMB reviewed safety data and agreed that the cumulative safety data from adults and adolescents enrolled in GBT440-031 and GBT440-007 supports the initiation of treatment of participants 4 to < 12 years old with voxelotor.

Part D: The DSMB has reviewed safety data from Part C and agreed that the cumulative data support the initiation of treatment in participants aged 2 to < 4 years. In addition, enrollment of participants aged 6 months to < 2 years will commence after Sponsor review of safety, tolerability, and PK data from ≥ 6 participants aged 2 to < 4 years who were treated with voxelotor for ≥ 28 days from Part D of this study or other GBT studies. The DSMB may be consulted if warranted.

3.8. End of Study

The end of study (EOS) is defined as the date when the last participant has completed all study procedures up to and including the final study/early termination visit as outlined in the Schedule of Assessments ([Appendix 1](#) for Part A, [Appendix 3](#) for Part B, [Appendix 5](#) for Part C, and [Appendix 7](#) for Part D).

3.9. Endpoints

3.9.1. Endpoints for Part A

3.9.1.1. Primary Endpoints

- Maximum observed concentration (C_{max}), area under the concentration-time curve from time zero to the time of the last quantifiable concentration ($AUC_{0\text{-last}}$), and area under the concentration-time curve from time zero extrapolated to infinity ($AUC_{0\text{-inf}}$) of voxelotor in whole blood

3.9.1.2. Secondary Endpoints

- C_{max} , $AUC_{0\text{-last}}$, and $AUC_{0\text{-inf}}$ of voxelotor in plasma and RBC

- The time of maximum concentration (T_{max}), terminal elimination half-life ($t_{1/2}$), percent Hb occupancy

3.9.1.3. Safety Endpoints

- TEAEs and SAEs
- Clinical laboratory tests, physical examination findings, vital signs, and ECGs

3.9.2. Endpoints for Part B

3.9.2.1. Primary Endpoints

- Change from baseline to Week 24 in Hb

3.9.2.2. Secondary Endpoints

- Proportion of days with SCD symptom exacerbation during the first 24 weeks of treatment.
- Change from Baseline to Weeks 21–24 in the SCDSM TSS; for each participant, the TSS will be computed as follows: The Baseline TSS is the average of the score during the 35-day Screening period; during the treatment period, the TSS is the average score each 4-week period on treatment. The 4-week periods are Weeks 1–4, 5–8, 9–12, 13–16, 17–20 and 21–24 (and follows similarly for participants whose participation exceeds 24 weeks).
- Change from baseline to Week 24 in LDH, indirect bilirubin and reticulocyte count
- Voxelotor PK (C_{max} , $AUC_{0\text{-last}}$, $AUC_{0\text{-inf}}$, $AUC_{0\text{-}24}$, $t_{1/2}$, accumulation ratio, blood/plasma ratio, RBC/plasma ratio, if appropriate), and percent Hb occupancy
- Change from baseline to 12 and 24 weeks in cerebral blood flow as measured by the time-averaged mean of the maximum (TAMM) TCD velocity

3.9.2.3. Safety Endpoints

- TEAEs and SAEs
- Clinical laboratory tests, vital signs, and ECGs

3.9.3. Endpoints for Part C

3.9.3.1. Primary Endpoint

- Change from baseline to 48 weeks in cerebral blood flow as measured by the TAMM TCD velocity

3.9.3.2. Secondary Endpoints

- Change from baseline to Weeks 24 and 48 in Hb, LDH, indirect bilirubin, and reticulocyte count

- Change from baseline to 24 weeks in cerebral blood flow as measured by the TAMM TCD velocity
- Time to initial Hb response, defined as change from baseline in Hb $> 1\text{ g/dL}$
- Whole blood and plasma voxelotor PK (C_{\max} , AUC, $t_{1/2}$), and percent Hb occupancy
- Proportion of participants with normal TCD flow velocity ($< 170\text{ cm/sec}$ by nonimaging TCD or $< 155\text{ cm/sec}$ by TCDi) at 48 weeks
Incidence of stroke and VOC during the study

3.9.3.3. Safety Endpoints

- TEAEs and SAEs
- Clinical laboratory tests, vital signs, and ECGs

3.9.4. Endpoints for Part D

3.9.4.1. Primary Endpoints

- TEAEs and SAEs

3.9.4.2. Secondary Endpoints

- Whole blood and plasma voxelotor PK (C_{\max} , AUC, $t_{1/2}$, if appropriate) and percent Hb occupancy
- Change from baseline to Week 24 and Week 48 in Hb, LDH, indirect bilirubin, and reticulocyte count
- Time to initial Hb response, defined as change from baseline in Hb $> 1\text{ g/dL}$
- Incidence of stroke and VOC during the study

3.9.4.3. Exploratory Endpoints

- Growth and development as assessed by change from baseline to Weeks 24 and 48 in height, weight, and head circumference

3.9.4.4. Safety Endpoints

- Clinical laboratory tests and vital signs

4. STUDY POPULATION

4.1. Inclusion Criteria

All participants must meet the following inclusion criteria:

1. Male or female with homozygous hemoglobin SS (HbSS) or hemoglobin S beta⁰ thalassemia (HbS β⁰ thal).
2. Age:
 - Part A – 6 to 17 years of age (Cohort 1 [12-17] and Cohort 2 [6-11] as defined in the Study Design)
 - Part B – 12 to 17 years of age
 - Part C – 4 to 17 years of age
 - Part D – 6 months to < 4 years of age
3. HU therapy:
 - Parts A, B, and C – A participant taking HU may be enrolled if the dose has been stable for at least 3 months with no anticipated need for dose adjustments during the study and no sign of hematological toxicity.
 - Part D – A participant taking HU may be enrolled if the dose has been stable for at least 1 month. Titration to the maximum tolerated dose (MTD) is allowed during the study.
4. Hemoglobin (Hb):
 - Part A – No restriction
 - Part B – Hb ≤ 10.5 g/dL
 - Part C – Hb ≤ 10.5 g/dL
 - Part D – Hb ≤ 10.5 g/dL
5. Written informed parental/guardian consent and participant assent has been obtained per institutional review board (IRB)/Ethics Committee (EC) policy and requirements, consistent with ICH guidelines.
6. Participants in Part B (only) of the study must complete a minimum of 14 days with ePRO to be enrolled. Investigator discretion will be used to determine if a participant who has previously been screen failed due to a lack of baseline ePRO data collection can be invited back for re-screening.
7. If sexually active and female, must agree to abstain from sexual intercourse or to use a highly effective method of contraception throughout the study period and for 30 days after discontinuation of study drug. If sexually active and male, must agree to abstain from sexual intercourse or willing to use barrier methods of contraception throughout the study period and for 30 days after discontinuation of study drug. Refer to Section 8.5.

8. Females of child-bearing potential are required to have a negative pregnancy test before the administration of study drug.
9. Sufficient venous access to permit collection of PK samples and monitoring of laboratory safety variables, in the opinion of the Investigator.
10. For Part C only: participants 12 to 17 years of age must have a TCD velocity \geq 140 cm/sec by nonimaging TCD or \geq 125 cm/sec by TCDi measured anytime during screening.

4.2. Exclusion Criteria

Any participant who meets one or more of the following criteria will be excluded from participation:

1. Any one of the following requiring medical attention within 14 days of signing the informed consent form (ICF):
 - Vaso-occlusive crisis (VOC)
 - Acute chest syndrome (ACS)
 - Splenic sequestration crisis
 - Dactylitis
2. Requires chronic transfusion therapy.
3. History of stroke or meeting criteria for primary stroke prophylaxis (history of two TCD measurements \geq 200 cm/sec by nonimaging TCD or \geq 185 cm/sec by TCDi).
 - For the potential modification, addition of approximately 20 participants enrolled in Part C, TCD \geq 170 cm/sec by nonimaging TCD or \geq 155 cm/sec by TCDi
4. Transfusion within 30 days prior to signing the ICF.
5. Renal dysfunction requiring chronic dialysis or creatinine \geq 1.5 mg/dL.
6. Hepatic dysfunction characterized by alanine aminotransferase (ALT) $> 4 \times$ upper limit of normal (ULN) for age.
7. Clinically relevant cardiac abnormality, in the opinion of the Investigator, such as:
 - Hemodynamically significant heart disease, eg, congenital heart defect, uncompensated heart failure, or any unstable cardiac condition.
 - An arrhythmic heart condition requiring medical therapy.
8. QTcF > 450 msec, congenital long QT syndrome, second or third degree heart block at rest (with the exception of asymptomatic Mobitz type I second degree heart block).
9. Received an investigational drug within 30 days or 5 half-lives, whichever is longer, of signing the ICF.
10. Heavy smoker (defined as smoking more than 10 cigarettes/day or its nicotine equivalent including e-cigarettes).

11. Unlikely to comply with the study procedures.
12. Other medical, psychological or addictive condition that, in the opinion of an Investigator, would confound or interfere with evaluation of safety and/or PK of the investigational drug, prevent compliance with the study protocol, or preclude informed consent.
13. Participants who do not have a TCD window (Part B and Part C only) (ie, participants who are unable to have a TCD due to skull ossification).
14. For Part C only, prior participation in Part B.
15. Active symptomatic COVID-19 infection.

In addition, for Part D only:

16. Body weight < 5 kg for 1 month prior to the screening visit and at the screening visit.
17. Any condition affecting drug absorption, such as major surgery involving the stomach or small intestine (prior cholecystectomy is acceptable).
18. History of malignancy within the past 2 years prior to treatment Day 1 requiring chemotherapy and/or radiation (with the exception of local therapy for non-melanoma skin malignancy).
19. Clinically significant bacterial, fungal, parasitic, or viral infection currently receiving or that will require therapy.
 - Participants with acute bacterial infection requiring antibiotic use should delay screening until the course of antibiotic therapy has been completed and the infection has resolved, in the opinion of the investigator.
 - Known active hepatitis A, B, or C infection or human immunodeficiency virus (HIV)-positive.
 - Known active malaria.

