To estimate appropriate doses to be evaluated in pediatric participants (6 months to < 12 years) with SCD, multiple doses of voxelotor were simulated by weight group (10 to < 20 kg and 20 to < 40 kg). The dose simulations were based on a voxelotor whole blood PPK model, including data from adults, adolescents, and children age 6 to 11 years old. The model used the same model structure (2-compartment model with first-order absorption) as the adult PPK model. The clearance (CL) and central volume (Vc) were scaled allometrically (exponents of 0.75 for CL and 1 for Vc) based on participant weights sampled from age-stratified normal distributions for children with homozygous SCD ([Thomas, 2000](#)). Summary exposure metrics (AUC, C_{max,ss}, and minimum drug concentration [C_{min,ss}]) in children (9 months to < 12 years) were compared to the interquartile range of exposures simulated for the equivalent dose in adolescent participants.

Weight-based groups were identified to target median exposures within the adolescent interquartile range. Based on simulations in the pediatric population, doses of 400, 600, and 900 mg, respectively, are supported to provide exposures similar to adolescent participants at 1500 mg. Participants with weights > 40 kg will receive the same dose as adolescent or adult participants.

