5.3. Clinical Assessments

Screening assessment must be conducted within 28 days prior to initiation of dosing for Part A, and within 35 days prior to initiation of dosing for Parts B, C, and D. Laboratory assessments, vital signs and physical examinations conducted on Day 1 predose may be conducted on Day -1. Refer to [Appendix 1](#), [Appendix 3](#), [Appendix 5](#), and [Appendix 7](#) for additional details.

Clinical assessments, including weight, vital signs, ECGs, AEs, and concomitant medications will be conducted at specified time points during the study (refer to [Appendix 1](#), [Appendix 3](#), [Appendix 5](#), and [Appendix 7](#)). Vital signs data to be collected include supine systolic and diastolic blood pressure, pulse rate, respiration rate and temperature (in °C). 12-lead ECGs will be collected in triplicate. Any other medical condition present at baseline should be followed during the study, and a change from the baseline status (intensity or frequency) should be reported as an AE if deemed clinically significant by the Investigator (refer to Section 9).

Height and weight will be recorded as outlined in [Appendix 1](#), [Appendix 3](#), [Appendix 5](#), and [Appendix 7](#). There is no weight restriction for Parts A, B, or C of the study. Height (in centimeters) and weight (in kilograms) should be measured with the participant's shoes off. Head circumference will be recorded in Part D as outlined in [Appendix 7](#).

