5.5. Eligibility Assessment

Eligibility assessment will be conducted during Screening and also prior to receiving study drug on treatment Day 1. If a participant is found to meet inclusion/exclusion criteria at the screening visit, but then has a clinically significant change in status prior to administration of the first dose of study drug (for example is hospitalized for sickle cell crisis), the participant should be withdrawn from the study. Re-screening may be considered at the discretion of the Investigator and in consultation with the Sponsor. Participants who re-screen will have all assessments redone except for iron testing (Parts A, B, and C only).

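### Low-severity wording error: read literally, Part D exclusion 16 leaves a child under 5 kg at screening eligible, although the protocol lists no dose below 5 kg

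*Protocol*

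**What the plan says.** Part D enrols children "6 months to < 4 years of age" (Protocol Section 4.1, criterion 2). None of the inclusion criteria sets a minimum weight. The only weight criterion is exclusion 16 in Section 4.2: "Body weight < 5 kg for 1 month prior to the screening visit and at the screening visit". The synopsis has the same wording, so it does not settle the meaning.

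The lead-in to Section 4.2 excludes anyone who meets at least one listed criterion. That rule works across the numbered criteria. It does not say that meeting half of one criterion is enough.

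Three other places bear on the point:

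- Section 7.1.3 sets the initial Part D dose from the weight at screening, using Table 3.
- The lowest row in Table 3 (Section 1.5.3) and in Table 8 (Section 8.2.3) is 5 to < 10 kg, with a full dose of 400 mg. Neither table has a row below 5 kg.
- Section 5.3 states: "There is no weight restriction for Parts A, B, or C of the study". Part D is left out of that sentence.

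**The concern.** An eligibility criterion and the dosing tables should share a lower limit, so that every child who passes screening has a listed dose. Both use the figure 5 kg here, but exclusion 16 attaches a time condition that the tables do not have. Taken at its word, the one-month clause can only narrow the exclusion: it rescues a child who is too light at screening if that child was heavier at some time in the prior month.

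What is at stake is whether a site that follows the text exactly could enrol a child whom the protocol gives no instruction for dosing. Children at the bottom of the weight range are also those with the least room for dose adjustment. A footnote to Table 8 allows only one dose reduction for children of 5 to < 10 kg who take the powder.

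**Working it through.** There is no sample size, power or alpha figure to reproduce. The check is a logical one, followed by a rough look at exposure.

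**Step 1. The criterion as a rule.** Let A mean that weight was below 5 kg for the month before screening, and B that weight is below 5 kg at screening. As written, the rule is: exclude if A and B.

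| A (prior month) | B (screening) | Excluded as written? | Dose in Table 3? |
|---|---|---|---|
| yes | yes | yes | not needed |
| no | yes | **no** | **none** |
| yes | no | no | 400 mg row, if under 10 kg |
| no | no | no | yes |

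The second row is the gap. As an illustration, a child who weighed 5.2 kg three weeks before screening and 4.7 kg at screening has A false and B true, and so is not excluded.

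**Step 2. Do other provisions close the gap?** Exclusion 17 covers "Any condition affecting drug absorption, such as major surgery involving the stomach or small intestine", and exclusion 19 covers "Clinically significant bacterial, fungal, parasitic, or viral infection currently receiving or that will require therapy". Exclusion 1 covers recent acute sickle cell events, and exclusion 12 relies on investigator judgment. These would catch some children who are losing weight through illness, but none is a weight floor. Section 5.5 adds a second look: "Eligibility assessment will be conducted during Screening and also prior to receiving study drug on treatment Day 1". Exclusion 16 refers only to the screening visit and the month before it, however, so re-applying the same sentence on Day 1 gives the same answer. Section 3.7 says "enrollment of participants aged 6 months to < 2 years will commence after Sponsor review", but that review concerns data from children aged 2 to < 4 years and is not a check on weight.

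**Step 3. Rough size of the exposure effect.** The protocol assigns no dose below 5 kg. *Assume* that a site gave the 400 mg of the lowest band. Section 1.5.3 scales clearance and volume allometrically ("exponents of 0.75 for CL and 1 for Vc"). With AUC = dose / CL and CL proportional to weight^0.75, AUC relative to a 5 kg child on the same dose is (5 / weight)^0.75.

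- 4.7 kg: (5 / 4.7)^0.75 = 1.05; dose per kg 400 / 4.7 = 85.1 mg/kg
- 4.5 kg: (5 / 4.5)^0.75 = 1.08; dose per kg 400 / 4.5 = 88.9 mg/kg
- With exponent 1, taken as an upper bound: 5 / 4.7 = 1.06 and 5 / 4.5 = 1.11

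For comparison, the spread that the plan already accepts within the 5 to < 10 kg band on 400 mg is (10 / 5)^0.75 = 1.68, or 400 / 5 = 80 mg/kg at the bottom against about 400 / 10 = 40 mg/kg near the top. The excess at 4.7 or 4.5 kg is small beside that. The scaling ignores enzyme maturation, which could matter in infants.

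**The case against.** The strongest reply is that the sentence names two times at which a single 5 kg floor applies, and that a site would read it so. Section 5.3, by naming only Parts A, B and C as unrestricted, implies that Part D was meant to have a floor. The dosing tables start at 5 kg, and dose comes from screening weight. Read together, these point to disqualifying any child below 5 kg at screening. This supports what was probably intended, and it is why the point is a wording slip rather than a design fault. It does not change what the criterion says when applied on its own, and no passage states the looser reading.

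A second reply is that the case hardly arises. The child must be at least 6 months old, have been at or above 5 kg within the month, and be below it at screening. The missing row would then stop dosing until someone asked. Both points stand, and they set the severity.

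A third is that the one-month element may be deliberate, since Section 7.1.3 also asks that a weight change be stable before the dose is adjusted. That is possible. Even so, a child below 5 kg at screening would be eligible with no listed dose, so the text would still need correcting.

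A reader might infer more: that the sponsor means to enrol children under 5 kg, or that the smallest children in general are let through. The documents do not support either. Section 5.3 and the tables point the other way, and a child below 5 kg both throughout the month and at screening is excluded on either reading.

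**Conclusion.** Exclusion 16 is wrong as written, at low severity. Followed literally, it keeps one kind of child eligible (below 5 kg at screening, not below 5 kg throughout the prior month) for whom Tables 3 and 8 list no dose, and no other criterion supplies a weight floor. This rests on reading 'and' as joining two conditions that must both hold, which is the plain sense of the sentence but not the only possible one.

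The likely result is a query from the site. A reader might see a risk of overdosing. The documents do not support that as a finding: the 400 mg figure used above is an assumption, and even under it the predicted AUC is only about 1.05 to 1.08 times that of a 5 kg child (1.06 to 1.11 with exponent 1). Nor is the absence of a separate Day 1 weight limit an error. Such a limit would be a new requirement, not a correction of this sentence. No endpoint, analysis or sample size depends on the point.

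**What to change.** In Section 4.2 and in the synopsis, reword exclusion 16 so that a body weight below 5 kg at the screening visit is sufficient by itself to exclude. Every child who passes on weight at screening then falls in a row of Table 3.

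The sponsor should decide what happens to the one-month element and say so. If it is also meant to exclude, replacing 'and' with 'or' is enough. That change would exclude, in addition, a child who was below 5 kg for the prior month but has reached 5 kg by screening (the third row of the table above), so it should be a choice and not a side effect. The wording should also say whether the condition means throughout the month or at any time in it.

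Optionally, the sponsor could apply the same floor at the Day 1 eligibility review, since Appendix 7 already collects weight on that day.

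The cost is a short edit in two places and at most a very few extra screen failures. Eligibility is tightened, not loosened.
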